1.1 What anatomical protocol should be used?

We have shown (1) that the sensitivity, in the first trimester, for the detection of major anomalies in unselected populations (19 studies, 115731 fetuses) is 46.10% (95% CI, 36.88–55.46%), representing 53.47% (95% CI, 43.42–63.37%) of all antenatally diagnosed ultrasound abnormalities. The detection rate for all abnormalities in unselected populations (14 studies, 97976 fetuses) was 32.35% (95% CI, 22.45–43.12%), while in high-risk populations (six studies, 2841 fetuses) it was 61.18% (95% CI, 37.71–82.19%). There was significant association ($P < 0.001$) between the sensitivity of first-trimester ultrasound and the use of an anatomical protocol for screening, with a trend suggesting that the more detailed the protocol, the greater the detection rate.

As part of the preparation for this proposal we have already conducted a systematic review of all available screening protocols (Table 1).

Table 1: Currently available screening protocols: summary table

| Anatomical Structure | Structure Required to be Visualized | Plane of Visualization | Supporting Protocols |
|---------------------------|--|----------------------------|-------------------------------|
| Skull/Brain | Cranial ossification (contour/shape) | Transverse | 14, 22-25 |
| | | Transverse + Coronal | 26, 27 |
| | | Longitudinal | 28 |
| | | No plane specified | 29-44 |
| | Choroid plexus filling lateral ventricles (butterfly sign) | Transverse | 14, 22-28, 33 |
| | | No plane specified | 31, 32, 34-40, 42, 43 |
| | Cerebral peduncles | Transverse | 23 |
| | Thalamus | Transverse | 27 |
| | | Mid-Sagittal | 33 |
| | | No plane specified | 42 |
| | Interhemispheric fissure/falx | Transverse | 14, 22, 24-26, 28, 30, 32 |
| | | No plane specified | 29, 33-35, 37, 39, 40, 42, 44 |
| | Posterior fossa | No plane specified | 43 |
| | Posterior fossa + demonstration of intracranial translucency | Mid-Sagittal | 22, 23 |
| | | Transverse + Mid-Sagittal | 33 |
| Intracranial Translucency | Longitudinal | 28 | |
| Cisterna magna | Transverse | 24 | |
| | Transverse + Mid-Sagittal | 33 | |
| Cerebellum | Transverse | 24 | |
| | No plane specified | 27, 32, 34, 38, 40, 42, 43 | |
| Face | Orbits | Transverse | 23, 24, 26, 28 |
| | | Coronal | 27 |
| | | Transverse or Coronal | 22 |
| | | No plane specified | 25, 31-33, 37-39, 41-44 |
| | Lenses | Transverse | 24, 26 |
| | | No plane specified | 39, 43 |
| | Anterior palate | Transverse | 23 |
| Mid-Sagittal | | 33 | |

| | | | |
|------------------------|--|---------------------------------|------------------------------------|
| | Nasal bones | Mid-Sagittal | 14, 26, 27, 33 |
| | | Sagittal | 23, 24 |
| | | Longitudinal | 28 |
| | | No plane specified | 31, 34, 37, 38, 43 |
| | Correct position of mandible | Mid-Sagittal | 26 |
| | | Transverse + Sagittal | 24 |
| | | Transverse or Coronal | 22 |
| | | No plane specified | 27, 33, 41, 42 |
| | Correct position of maxillae | Transverse + Sagittal | 24 |
| | | Transverse or Coronal | 22 |
| | | No plane specified | 41, 42 |
| | Facial profile | Mid-Sagittal | 22, 26, 27 |
| | | Sagittal | 23, 24 |
| | | Longitudinal | 28 |
| No plane specified | | 25, 31-33, 37-39, 41 | |
| Ears | No plane specified | 43 | |
| Retronasal triangle | Coronal | 23, 28, 33 | |
| Upper and/or lower lip | Coronal | 24, 26 | |
| | No plane specified | 22, 25, 28, 41, 43 | |
| Spine | Presence/regularity of vertebrae from cervical to sacral regions | Longitudinal | 14, 23, 25, 28, 36 |
| | | Longitudinal + Transverse | 22, 26, 27, 38, 40-42 |
| | | Sagittal + Coronal + Transverse | 24 |
| | | No plane specified | 32, 33, 39 |
| | Intact, continuous overlying skin | Longitudinal | 23, 25 |
| | | Longitudinal + Transverse | 38, 40, 42 |
| Thorax/Chest | Shape of the thorax | Sagittal | 26, 37 |
| | | No plane specified | 24, 27, 33, 34, 39 |
| | Lung fields | Transverse | 24 |
| | | No plane specified | 25 |
| | Diaphragmatic continuity | Transverse | 22, 24, 26 |
| | | No plane specified | 25, 27, 31-33, 35, 43 |
| Heart | Situs evaluation | Longitudinal | 28 |
| | | No plane specified | 26, 27, 30, 33, 34, 36, 38, 40, 41 |
| | | Transverse | 22, 23, 43 |
| | Heart area in relation to chest | Longitudinal | 28 |
| | | Transverse | 23 |
| | Cardiac axis | Transverse | 26, 34, 38, 40, 43 |
| | | No plane specified | 29 |
| | Four-Chamber view (with AV valve offsetting) | Transverse | 14, 22-24, 26, 43 |
| | | Longitudinal | 28 |
| | | No plane specified | 25, 27, 32-42, 44, 45 |
| | Outflow tracts (pulmonary artery, aorta, SVC – 3 vessel view) | Transverse | 23, 24, 43 |
| | | Longitudinal | 28 |
| | | No plane specified | 22, 27, 33, 37-39, 41 |
| | Aortic Arch | No plane specified | 40, 43 |
| Fetal heart rate | No plane specified | 26, 27, 32, 34, 38, 40 | |
| Abdomen | Presence of stomach in left quadrant | Transverse + Sagittal | 14, 22 |
| | | Transverse + Coronal | 26 |
| | | Transverse | 24 |
| | | Longitudinal | 28 |
| | | No plane specified | 23, 25, 27, 29, 30, 32-44 |
| | Presence of bladder in fetal pelvis | Transverse + Sagittal | 14, 22, 24 |
| | | No plane specified | 23, 25-27, 29-34, 36-45 |

| | | | |
|----------------------------|--|-----------------------|---------------------------------|
| | Bilateral presence of kidneys | Coronal + Transverse | 24 |
| | | Coronal | 26, 27 |
| | | No plane specified | 22, 23, 31-33, 35-43, 45 |
| | Intact abdominal wall with demonstrated umbilical cord insertion | Transverse + Sagittal | 14, 22 |
| | | Transverse | 28 |
| | | No plane specified | 23-27, 30-44 |
| | Bowel echogenicity | No plane specified | 23, 24, 43, 45 |
| | Gallbladder | No plane specified | 43 |
| External genitalia | No plane specified | 32 | |
| Bifurcation of portal vein | Transverse | 24 | |
| Limbs | Symmetry and adequate views of long bones of all 4 limbs | No plane specified | 22-27, 29-45 |
| | | Longitudinal | 28 |
| | | Transverse + sagittal | 14 |
| | Bilateral feet visible with correct orientation | Transverse + sagittal | 14 |
| | | Longitudinal | 28 |
| | | No plane specified | 22-27, 31, 33-35, 37, 39, 41-45 |
| | Bilateral toes visible | No plane specified | 23, 24, 32, 37, 39 |
| | Bilateral hands visible with correct orientation | Transverse + sagittal | 14 |
| | | Longitudinal | 28 |
| | | No plane specified | 22-27, 31, 33-35, 37, 39, 41-45 |
| | Bilateral fingers visible | No plane specified | 23, 24, 29, 32, 37, 39 |

Notes: excluded assessment of soft markers (eg. NT), Doppler investigations and fetal biometry.

As part of this study we will undertake a wide scoping and consulting exercise to inform a consensus meeting in order to determine the best ultrasound protocol to use (see WP 2). This is important because detection rates for different types of anomalies differ significantly (see Table 2).

Table 2: Classification of fetal anomaly detection in the first trimester, based on (13, 14, 27, 28).

| Anomalies Considered to be Nearly Always Detectable (approx. 90-100%) | Anomalies Considered Potentially Detectable (approx. 2-90%) | Anomalies Considered to be virtually undetectable (<2%) |
|--|---|---|
| Acrania Anencephaly Alobar holoprosencephaly Encephalocele Ectopia cordis Exomphalos Gastroschisis Megacystis Body stalk anomaly | Facial clefts Hydrocephalus Spina Bifida Skeletal Dysplasias Arthrogyposis Limb reduction Polydactyly Septal Defect Transposition of the Great Arteries Double-outlet right ventricle Aortic Coarctation Hypoplastic left heart syndrome Valvular Disease Multicystic Kidneys Dandy-Walker Syndrome | Corpus callosum agenesis Bladder exstrophy Congenital cystic adenomatoid malformation Extralobar sequestration Cerebellar hypoplasia Duodenal atresia Anal atresia Bowel obstruction Duplex kidneys Hydronephrosis Ovarian cyst Fetal tumours (nasopharyngeal, cardiac and sacrococcygeal) |

1.2 What is the best gestational age to screen?

Studies suggest that anatomical visualization improves significantly with increasing gestational age between 11 and 14 weeks, impacting in particular on the examination of the fetal heart and kidneys. The most recent and largest studies that address this issue (see Table 3) suggest that later screening has advantages both for overall anatomical assessment; and for detection of specific anatomical views.

Table 3: Effect of gestational age / fetal size on detection rates for fetal anomalies

| Souka et al. (46): | | | | |
|--------------------|---------|---------|---------|---------|
| CRL | 45-54mm | 55-64mm | 65-74mm | 75-82mm |
| | | | | |

| (GA) | (11 ^{+0-11⁺⁶}) | (12 ^{+0-12⁺⁵}) | (12 ^{+6-13⁺³}) | (13 ^{+4-14⁺⁰}) |
|-------------------------------------|-------------------------------------|-------------------------------------|-------------------------------------|-------------------------------------|
| Complete anatomy excl. cardiac exam | 65% | 84% | 93% | 96% |
| Complete anatomy incl. cardiac exam | 22% | 43% | 56% | 67% |
| 4-Chamber view | 67% | 86% | 94% | 98% |
| 3-Vessel view | 25% | 46% | 58% | 67% |
| Luchi et al. (47): | | | | |
| 4-Chamber view | 87% | 98% | 100% | |
| 3-Vessel view | 64% | 86% | 94% | |
| Kidneys | 36% | 62% | 89% | |
| Cerebellum | 12% | 66% | 87% | |

However, this improved detection rate with advancing gestation needs to be balanced against the later detection, and the impact on screening for chromosomal anomalies. We will conduct a sensitivity analysis of screening performance for anatomical defects by gestational age and use a model to assess optimal gestational age for the detection of both anatomical and chromosomal abnormalities for those women who opt to screen for both.

1.3 Is there a preferred method of scanning (transabdominal (TA) / transvaginal (TV))?

Most reported studies use a combination of TA and TV ultrasound. Findings from studies evaluating fetal organ detection suggest that optimal visualization rates are obtained with a combination of TA and TV ultrasound(42). For TA, raised BMI, fibroids or retroversion of the uterus will decrease image quality (37, 42, 48). In contrast, TV ultrasound provides much higher resolution, but has the disadvantage of limited probe manoeuvrability (48) and reduced acceptability (37, 49). A detailed comparison between sensitivities from studies using one of the three methods (TA, TV or combination of both) will be undertaken.

1.4 What specific anomalies are amenable to first trimester detection and at what detection rates?

Some conditions seem nearly always detectable in the first trimester, others never identifiable and some can be diagnosed, depending on maternal, fetal, sonographer and equipment factors (13, 14, 27, 28). Thus, first-trimester anomaly screening may need to be considered as an adjunct, as opposed to a replacement of ultrasound examination at later gestational ages. Thus expectations and future objectives for first-trimester anomaly screening must be tailored to the type of anomalies amenable to reliable detection at this gestational age. At present, the literature has little data focused on the sensitivity of ultrasound at 12 weeks of gestation for individual anomalies. This will need to be further explored in order to identify which conditions should be specifically targeted by a national first trimester anomaly screening program.

1.5 What are the false positive rates for these different conditions?

It must be highlighted that the majority of existing studies do not report false positive rates. One of the inevitable consequences of first trimester screening is the offer of early termination of pregnancy when major anomalies are seen. There is a self-evident concern regarding offering termination of pregnancy after first trimester anomaly screening without a full understanding of a false positive diagnosis. It is not always easy to work out what a false positive is, as anomalies evolve: for example, a significant proportion of megacystis or bowel-only exomphalos resolve spontaneously with advancing gestation. Hence, it is critical not only to understand the false positive rate in first trimester screening, but also what types of anomalies are most likely to resolve spontaneously.

1.6 How should data on fetal abnormalities be reported or "counted"?

This is not straightforward as the number of structural abnormalities is reported in various ways in different studies. For example, studies variably report the number of fetuses affected by one or more anomalies in the numerator, with normal fetuses in the denominator; but as fetal anomalies may be multiple, other authors count the number of fetal anomalies. Even what constitutes 'one detected structural abnormality' is not defined uniformly: for example, bilateral defects (such as bilateral renal agenesis) are counted variably as one or two individual structural anomalies. Secondly, fetuses diagnosed with a syndrome, based on the findings of multiple malformations on ultrasound, are variably reported as having one anomaly (the syndrome) or several anomalies (the constituent defects). Thirdly, in several studies, a single fetus may be attributed to having

multiple anomalies within one organ system (eg. 'multiple skeletal abnormalities'). In this case, the fetus could be considered to have one structural ("a skeletal") abnormality. Finally, soft markers for fetal aneuploidy (including increased NT and absent nasal bone) are sometimes included as anomalies; these will be excluded in this review as they do not constitute fetal defects per se.

As can be seen there are several subtleties and uncertainties that require definitions and proposals will be made on the basis of literature review and consensus, including with the experts in fetal screening.

WP 2. Survey of the current screening environment and impact on NICE care pathway

A national scoping exercise has identified four broad categories of routine first trimester ultrasound scans practiced in the UK:

1. Basic first trimester ultrasound: Confirmation that the fetus is alive, accurate dating by measurement of fetal CRL and detection of multiple pregnancy
2. Basic first trimester ultrasound and measurement of fetal nuchal translucency (NT): as above, PLUS screening for chromosomal abnormalities usually in conjunction with first trimester maternal serum biochemistry
3. Basic first trimester ultrasound, measurement of NT and assessment of the fetal anatomy: as above, PLUS purposeful assessment of fetal anatomy with the aim of diagnosing major fetal abnormalities
4. Detailed fetal first trimester anatomical ultrasound: often reserved for targeted screening due to a previous abnormality or other risk factor, this is routinely undertaken in some UK centres and includes more detailed anatomical assessment.

We will conduct a nationwide survey of all maternity units to establish

- Screening protocols
- Where screening takes place (hospital, primary care, etc.)
- Whether first-trimester anatomy scanning is offered irrespective of choice for aneuploidy screening
- The impact of suspected abnormality (change from the NICE antenatal care pathway)

Management of pregnancies which screen positive are not covered in current UK clinical guidelines. We will combine this information with a systematic literature review to create possible management pathways.

WP 3: Consensus procedure to develop a protocol for the first trimester scan

In preparation for this step the detailed systematic reviews and survey results will be available. Given the large range of protocols available, the limitations from existing screening studies described and the need to create such a protocol in the light of the ultrasound scanning resource available, it is unlikely that guidance can be established based on research-based evidence alone. In order to capture interpretation of experts in the field, we will use the background protocol information to undertake a consensus procedure in order to unify individual opinions into a group consensus. This will consist of our expert panel as well as other experts in the field and lay representatives. Web-based tools (REDCap) will be used to gather the views of a range of professional stakeholders on the elements of the screening test, design of a screening trial, and the feasibility of population screening. Further methodological details regarding question development, selection and size of participant pool, analysis of iteration output and definitions of group consensus will be determined as part of the study and with adherence to recommendations from HTA guidance on consensus development methodology) (50).

A series of structured statements developed on the basis of our extensive literature review, which will require ranking of significance using a Likert scale. These results will be summarized using measures of central tendencies and levels of dispersion; statements will be fed back to participants with increasing detail over multiple rounds. With each iteration, the participants will be allowed to revise their opinion in light of the group feedback until relative consensus has been reached.

The issues we expect to address using this methodology include optimal gestational age for first trimester anomaly screening, anomalies which should be targeted, details of screening protocols including definition of

standard anatomical views and time to be allocated for screening. The issue of how first trimester screening should be developed in relation to its current second trimester counterpart will be considered. Discussions regarding the usefulness of developing a basic first trimester screening protocol alongside a more detailed protocol and the clinical situations where these might be beneficial will also be undertaken.

Finally, it is critical that alongside a standardised protocol, we have auditable standards combined with a quality assurance program for first trimester anomaly screening. This will be a key to the initiation and maintenance of a standardised and reproducible system – whether as part of a trial or implementation of first trimester anomaly screening across the UK.

There are no current quality control systems described in the literature that are specific to first trimester anomaly screening, but our group has developed score-based quality assessment tools for the purposes of sonographer teaching and for monitoring the skills of existing sonographers in the second trimester as well as for the measurement of fetal CRL and NT (51-53). We are currently evaluating the feasibility and reliability of using such a system for first trimester anomaly screening, and will publish such a scoring system as part of this project.

WP 4: Economic analysis and value of information (Vol)

4.1. Economic analysis of screening and intervention protocols

After reviewing the health economic literature we will identify the most appropriate modelling framework, model structure, key study parameters and potential measures of outcome. Some of the co-applicants (including the PI) are currently constructing a model to estimate the cost-effectiveness of late-pregnancy ultrasound screening (HTA 15/105/01). Whilst there is obvious overlap, there are also substantially different issues involved in the early screening model (see below), negating simple duplication. However, we anticipate being able to use some of the parts of the outline model as a starting point.

The model we develop will estimate the costs and outcomes of first trimester anomaly screening protocols and of current practice. An NHS and social services cost perspective will be taken in the first instance, and a wider societal perspective considered should data permit. The potential outcomes of first trimester anomaly screening are complex, multifaceted, and ethically sensitive with implications for both parents and infant. Specifically, a standard 'cost per QALY' approach might not be appropriate in this context as a decision to terminate a pregnancy will lead to a lifetime loss of QALYs, yet may be the desired maternal / couple's outcome. We are acutely aware of the sensitivities involved and so our analysis will acknowledge this and, in line with other studies in the field, we will seek to report separate outcomes using a cost-consequence framework (54). Specifically, we will explore outcomes from the perspectives of the mother, infant and (if data permit) both parents.

We hypothesise that earlier detection of a major anomaly could alter women's preferences for continuing a pregnancy and so will construct our model to simulate the impact on the pregnancy termination rate and the number of babies born with a major anomaly. An increased risk of miscarriage from invasive testing following a false positive early screen will also be considered. Equally important is the impact on parents. The psychological sequelae of terminating a pregnancy for a major anomaly are significant and any additional burden should be reflected (10, 11, 55, 56). Furthermore, the potential for false positive results with early screening and the associated anxiety and morbidity from additional invasive testing must also be considered. In contrast, earlier anomaly detection and intervention may avert some of the distress, and may avoid the additional pressures that parents feel to reach a decision about their pregnancy before the 24-week legal termination limit (55). Also, and should a termination be chosen, an earlier procedure may expose women to less physical harm than a later procedure. We plan to explore the likely net impact of all of these consequences upon maternal and parental utility during the pregnancy.

We foresee a need to compare variants of protocols (with different anatomical specifications / screening modalities and personnel / interventional pathways) and expect to operationalise these as alternative comparators within a decision tree model covering each of the three trimesters to birth. Within each trimester, the model will be structured for any anomaly screening results, related prevalence and sensitivity/specificity and intervention pathways, and will be populated with data on associated event

probabilities, costs, and parental and infant payoffs. Separate outcomes will be presented using the decision tree and will include births with a major anomaly, and maternal and parental utility during the pregnancy (expressed as quality adjusted life years (QALYs)). At this stage, we anticipate a paucity of data on the false positive rate (and hence specificity) of tests. The statistics will also vary by anomaly. Where data are not forthcoming we will seek expert opinion using a structured elicitation technique (e.g. SHELF) (57).

If the hypotheses above are correct, the implications of first trimester anomaly screening will extend beyond the pregnancy. For example, there may be long term cost-savings for the NHS and social services as well as a reduction in the parental burden of caring for a child born with a major anomaly. However, the notion that these benefits are realised through an increase in the number of pregnancies being terminated is ethically challenging. Indeed, the likely preferences of society for such a program are unclear. This in turn raises questions about the use of conventional cost-utility analyses whereby results are interpreted within the context of society's valuation of a QALY (54, 58). Although our primary approach will take the form of a cost-consequence analysis, we will also calculate incremental cost-effectiveness ratios, but would emphasise that in the light of the sensitivities discussed above, that these should be interpreted with caution.

Protocol alternatives and input parameters for the model will be informed by WPs 1, 2, and 3 as well as by supplementary literature searching and expert elicitation. We will utilise the planned national survey to elicit information on pregnancy termination rates with and without first trimester anomaly screening and will interrogate the Department of Health's termination statistics. Cost data will be sourced from administrative datasets, hospital finance departments, and the published literature. Model parameters will be entered as distributions and the resulting simulated costs and outcomes of each alternative will be compared to rule out dominated and extended dominated protocols. Incremental cost-effectiveness ratios (and/or net health/monetary benefit) will be computed for the remaining protocols and a VoI analysis conducted. These analyses will be conducted for various outcomes (including the number of births with an anomaly, and maternal quality adjusted life years) so as to make clear the social value judgements that arise when outcomes for different affected parties are considered. As a secondary analysis, we will also perform these works using the long-term cost and QALY framework, if viable.

Our intention will be to use the individual cost-effectiveness outcomes modelled (for example cost per live births with an anomaly averted or cost per maternal QALYs gained) in separate VoI analyses, which will also provide evidence regarding any recommendation about subsequent research. The cost-consequence approach to the economic analysis will allow the potential implications of the policy for the various affected parties (the babies, parents, and wider society) to be fully quantified and reported separately.

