4.2. Value of Information (VoI) analysis

Using the model's facility for probabilistic sensitivity analysis, we will calculate the expected value of perfect information (EVPI) and partial perfect information (EVPPI) and if either suggests value from future research, we will explore the expected value of sample information (EVSI), expected costs, and the expected net gain of sampling (ENGS) for various trial designs and sample sizes.

VoI analysis is complicated by the inability to calculate a single meaningful incremental cost per QALY gained from the screening intervention. We will, therefore, conduct these from the outcome perspectives of the mother, both parents, and if appropriate, from society too. The exact specification will be determined prior to analysis, but may, for example, in the case of the mother and parental perspectives, lead to the outcome being dichotomised into 'desirable' or 'undesirable', where a desirable outcome is one where a fetus is either carried to term or terminated in accordance with the wishes of the parent(s). Thus, the driver for 'undesirable' outcomes will be a function only of the false positive and negative rate of the screening test, thereby avoiding any social value judgements associated with the decision itself. The EVSI will then be interpreted as the expected gain in 'desirable' outcomes from additional information yielded from a trial. The cost and EVSI from alternative trial designs can then be compared in stepwise manner, excluding dominated and extended dominated options.

WP 5: Determining the final study design

We will draw together the findings and recommendations from the project, and, if appropriate, outline the design of plausible prospective studies. The Vol analysis will be rerun to predict the expected net gain of sampling (ENGs) of these. Where appropriate, this will include identifying the most efficient sample size for such studies, the range of sample sizes yielding a positive ENGs, and comparisons with the sample size yielded from a traditional power calculation.

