This work package is a new addition to version 9 of the protocol and was developed in response to findings from the work undertaken in WP1 and WP2. The nationwide survey of current ultrasound practice in England has shown that at present 75% of NHS Trusts routinely assess fetal anatomy in the first trimester, despite the absence of national policy. However, there is significant variation in practice seen between trusts regarding the anatomical structures evaluated in the first trimester, the anatomical image views obtained by sonographers routinely, the amount of time spent on scanning, and the training provided to sonographers.

Given that many trusts are already performing some form of first trimester anomaly scan, it is now feasible to use UK specific data (collected routinely by NCARDRS) from these ultrasound units in order to model the impact of the first trimester anomaly scan on the timing of fetal anomaly diagnoses, the timing of investigations (such as CVS/amniocentesis) and the timing of termination of pregnancy. Ultimately, this should allow us to determine whether trusts performing a routine first trimester anomaly scan are able to provide their patients with an earlier diagnosis than those trusts which do not offer this service, what system factors are associated to allow this, and whether this has any impact on patient outcomes. This data will be used in conjunction with the international literature-based data collected in WP1 to develop a more accurate and precise health economics model in WP4.

This work involves a collaboration between our group, NCARDRS and PHE. It will involve two members (AP and research fellow, JK) to obtain honorary research contracts from PHE and for the work to be formally approved by research ethics committee.

WP 7: Determining the acceptability of the early anomaly scan amongst women and their partners

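### In the example VoI outcome, a pregnancy lost after invasive testing is undesirable by definition, yet the stated driver of undesirable outcomes has no term for it

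*Protocol*

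**What the plan says.** All of this is in section 6 (Research Plan) of the protocol.

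- **WP 4, 4.1, harms of testing.** Procedure-related miscarriage is named once: "An increased risk of miscarriage from invasive testing following a false positive early screen will also be considered". The other harm of testing is also raised alongside false positives: "the associated anxiety and morbidity from additional invasive testing must also be considered". The consequences then feed into utility: "We plan to explore the likely net impact of all of these consequences upon maternal and parental utility during the pregnancy".
- **WP 4, 4.1, model structure.** In each trimester "the model will be structured for any anomaly screening results, related prevalence and sensitivity/specificity and intervention pathways". Current practice is also modelled: "The model we develop will estimate the costs and outcomes of first trimester anomaly screening protocols and of current practice".
- **WP 4, 4.2, example VoI outcome.** The exact specification is deferred until before the analysis. For the mother and parental perspectives the protocol gives an example, a two-state outcome. The desirable state is one where "a fetus is either carried to term or terminated in accordance with the wishes of the parent(s". The driver of undesirable outcomes "will be a function only of the false positive and negative rate of the screening test". EVSI is then to be read as the expected gain in desirable outcomes.
- **WP 6.** Registry data are to show how the early scan affects "the timing of investigations (such as CVS/amniocentesis", and these data feed the economic model.

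**The concern.** The definition and the driver in 4.2 do not agree. The definition sorts pregnancies by how they end. The driver sorts them by whether the screening result was wrong. The two part company when a pregnancy that the parents had not chosen to end is lost after an invasive test: the outcome is undesirable even where the screening result was correct.

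At stake is which parameters the VoI analysis can see. A two-state outcome driven by error rates alone assigns no value to learning more about uptake of invasive testing or about the procedure's loss probability. Yet 4.1 names this loss as a consequence to be weighed, and WP 6 expects the early scan to bear on when such tests are done. A VoI analysis meant to guide the design of a future study should not fix a named harm at zero, or at a constant, through its choice of wording.

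**Working it through.** The protocol gives no procedure-loss rate, test uptake or false positive rate, so it has no figure of its own to reproduce. The check is mainly textual.

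**1. Endings set against the definition and the driver (4.2)**

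| Ending | By the definition | By the driver |
|---|---|---|
| Carried to term, or terminated as the parents wish | Desirable | No contribution |
| Ending against the parents' wishes because the screen was wrong | Undesirable | Carried by the error rates |
| Lost after invasive testing, false positive screen | Undesirable | Enters only indirectly, through the false positive rate |
| Continuing pregnancy lost after invasive testing, true positive screen | Undesirable | Nothing: the result was correct |

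The last row is the contradiction.

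**2. The missing term**

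Let p be prevalence, Se sensitivity, FPR the false positive rate, u the uptake of invasive testing and l the loss probability. Losses per woman after the early scan are

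u × l × [p × Se + (1 − p) × FPR].

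Neither u nor l is an error rate of the screening test. One could argue formally that Se = 1 − false negative rate, so the true positive part can also be written through an error rate. That works only if u and l are fixed constants. On either reading they are not uncertain inputs to the outcome, so resolving them changes nothing on the outcome side, and their EVPPI and EVSI contribution there is zero by construction. Uptake could still enter through costs.

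**3. Gross scale (illustration only)**

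Inputs from the protocol: 203.35 non-chromosomal anomalies per 10,000 births (section 3); first-trimester sensitivity 32.35% for all anomalies and 46.10% for major anomalies, unselected populations (WP 1, 1.1). Assumed: FPR 0.1% to 1%, uptake 50%, and loss 0.1% to 1% per test, with uptake and loss the same in both groups.

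Per 100,000 women:

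- Affected: 2,033.5. Unaffected: 97,966.5.
- True positives: 2,033.5 × 0.3235 = 658 and 2,033.5 × 0.4610 = 937.
- False positives: 97,966.5 × 0.001 = 98 and 97,966.5 × 0.01 = 980.
- True positive share of early screen positives: 658/(658 + 980) = 40.2% to 937/(937 + 98) = 90.5%. If the FPR were 2%, with sensitivity 46.10%: 937/(937 + 1,959) = 32.4%.
- Losses in true positives: 658 × 0.5 × 0.001 = 0.33 to 937 × 0.5 × 0.01 = 4.7.
- Losses in false positives: 98 × 0.5 × 0.001 = 0.05 to 980 × 0.5 × 0.01 = 4.9.

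In gross terms, then, true positives are not a negligible source of loss beside the group that 4.1 names.

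**4. Why this is not a bias estimate**

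The 46.10% is stated to be 53.47% of antenatally diagnosed anomalies, which implies 46.10/53.47 = 86.2% antenatal detection overall. If that total does not change, many tests in true positives are moved earlier rather than added. The increment over current practice needs the second-scan losses under each strategy, and the protocol gives nothing from which to compute them.

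**The case against.** Two stronger readings are tempting.

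*That losses in true positives and under current practice are not counted in the economic model.* A reader might infer this because 4.1 names only the false positive group. The document does not support it. The sentence is additive, not exclusive, and it concerns an increased risk, for which false positives at a new scan are a natural first example. The tree is planned for any screening result, with intervention pathways and event probabilities across three trimesters, and current practice is modelled. It can hold these losses. The WP 6 data on test timing point the same way.

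*That procedure loss is left out of the VoI altogether.* This also goes too far. The two-state outcome is offered as an example with its specification deferred. Separate VoI analyses are planned on other outcomes, including maternal QALYs, which are to reflect the consequences listed in 4.1. Model parameters enter as distributions, so a loss probability in the tree would be available to those analyses.

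It can also be said that procedure-specific loss rates and a list of EVPPI parameters belong in a later analysis plan. That is fair, and their absence is not the point made here.

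What remains is narrow: the one worked specification for the mother and parental perspectives contradicts itself. The planned VoI on anomaly births averted would not repair it, since a procedure-related loss in a true positive would count there as a birth averted. Maternal QALYs could capture the loss, but in a different analysis.

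**Conclusion.** The contradiction in 4.2 is real and follows from the text alone, without any assumed figure. If the example is adopted as written, losses of continuing pregnancies after a true positive screen add nothing undesirable, and uncertainty in uptake and loss has no value on that outcome. It also sits badly with 4.1, which names procedure-related miscarriage as a consequence to be considered.

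The finding is limited to that example outcome. The illustration (true positives 40% to 91% of early screen positives; 0.3 to 4.7 losses per 100,000 women in that group) shows gross scale only. It rests on assumed false positive, uptake and loss rates and on equal uptake and loss in both groups. It also applies a non-chromosomal prevalence to sensitivities reported for other sets of anomalies, and it counts every true positive, including those in which termination is later chosen. The net effect between strategies may be much smaller, and its direction is unknown. The point is worth correcting before the VoI specification is fixed, because it determines which parameters can drive that analysis.

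**What to change.** - **In 4.2:** classify loss of a continuing pregnancy after invasive testing as undesirable. Replace the error-rates-only driver with a function of the false positive rate, the false negative rate, test uptake and the procedure-related loss probability. Enter the last two as distributions and include them in EVPPI. The stated purpose of the example, to avoid value judgements about the parents' decision, is kept, because such a loss is not a decision.
- **In 4.1:** align the miscarriage sentence with the planned tree by stating that procedure-related loss is modelled after any screen-positive result, true or false, in each strategy including current practice.

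The cost is a few sentences and the sourcing of two further parameters, for which evidence or structured elicitation may be needed, as the protocol already foresees for the false positive rate.
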